SPIN-SSLED Feasibility Measures: The aim of the SPIN-SSLED Feasibility Trial is to collect data related to the study's *process*, in order to assess the feasibility of the steps that need to take place as part of the full-scale RCT, including *required resources and management* (e.g., personnel and data management issues) and *scientific aspects* (e.g., acceptability, outcome assessments), as well as to obtain feedback on possible ways to improve the training program. Data will be used to determine whether it is feasible to carry out a full-scale trial, or whether changes need to be made to the trial design or training program. The feasibility trial outcomes related to process and resources will be assessed throughout the duration of the feasibility trial, and leader feedback will be obtained upon completion of the program.

The collected measures of feasibility include:

- How well the enrolment and randomization procedure work;
- The percentage of eligible group leaders who consent to participation;
- Personnel requirements to call enrolled leaders and help them with accessing the SPIN-SSLED Program online data collection platform;
- Challenges for study personnel;
- Technological performance of the videoconferencing system

We will also evaluate the degree to which the SPIN-SSLED Program is delivered with a high level of fidelity to the program manual. To do this, all SPIN-SSLED sessions will be audited for fidelity by two members of the research team. We will use standard methods for evaluating intervention fidelity,³⁵ including observation of entire sessions for a randomly selected sample of 25% of video-recorded sessions. Raters will evaluate adherence to each session's goals and content. Consistent with best-practice recommendations for assessing treatment fidelity,³⁵ this will be done using a checklist coding system based on a standardized format and adapted for the specific components of the SPIN-SSLED Program manual.

Finally, individual interviews will be conducted upon completion of the 13-modules to assess the accessibility of the intervention, barriers to participating, and user feedback, as well as to explore leaders' experience of taking part in the intervention. Participants who have completed any of the 13 modules will be asked to participate in the interviews.

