SPIN-SSLED Program Outcome Measures: In the planned full-scale randomized controlled trial (RCT) that will follow our feasibility trial, we will evaluate whether the SPIN-SSLED Program is effective in improving SSc support group leaders' self-efficacy for carrying out their leader role (primary) and if it reduces burnout, improves emotional well-being, and improves health-related quality of life (secondary). In the SPIN SSLED Feasibility Trial, outcome measures will be evaluated at the time of random allocation to a SPIN-SSLED Program training group and after completion of the Program (3 months post).

- The Scleroderma Support Group Leader Self-efficacy Scale (SSGLSS) was developed by our research team to measure support group leader self-efficacy for performing leader tasks. Initial items were extracted from previous measures developed for leaders of cancer support groups.³⁶⁻³⁸ All items were reviewed by our research team for relevancy and repetitiveness, and edited for clarity. Additional items were generated to reflect content important to SSc not included in the

initial item set. Items were reviewed iteratively by all members of the research team until a consensus was reached. The final 32-item scale is scored on a 1-6 Likert scale (1=*strongly disagree*; 6=*strongly agree*).

- **Burnout** will be assessed with the Oldenburg Burnout Inventory (OLBI).^{39,40} The OLBI is a 16-item measure of burnout that assesses levels of exhaustion and disengagement in work populations. Items were adapted and reviewed by project investigators for use within the support group leader population. Items are scored on a 4-point scale from 1 (strongly disagree) to 4 (strongly agree)
- **Emotional distress** will be assessed with the PHQ-8.^{41,42} The PHQ-8 items measure depressive symptoms over the last 2 weeks on a 4-point scale, ranging from 0 (not at all) to 3 (nearly every day) with higher scores indicating more depressive symptoms. The PHQ-8 performs equivalently to the PHQ-9,⁴¹ which is a valid measure of depressive symptoms in leaders with SSc.⁴²

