- **Leader-reported health status** will be measured using the 29-item Patient Reported Outcomes Measurement Information System (PROMIS-29) profile version 2.0. The PROMIS-29 measures 8 domains of health status with 4 items for each of 7 domains (physical function, anxiety, depression, fatigue, sleep disturbance, social roles and activities, pain interference) plus a single item for pain intensity. Items are scored on a 5-point scale (range 1-5), with different response options for different domains, and the single pain intensity item is measured on an 11-point rating scale. Higher scores represent more of the domain being measured; that is, better physical function and ability to participate in social roles and activities, but higher levels of anxiety, depression, fatigue, sleep disturbance, pain interference, and pain intensity. Total raw scores are obtained by summing item scores for each domain, which are converted into T-scores standardized from the general US population (mean=50, SD=10). The PROMIS-29 version 2.0 has been validated in SSc.^{43,44}

Harms/Adverse events: The present study is of minimal risk. We do not anticipate that there will be any adverse events from participating in the leader training sessions.

Sample size: Guidance on appropriate sample size for feasibility trials varies substantially in the published literature. Published guidelines⁴⁵ suggest that approximately 10% of the estimated sample size for the full-scale RCT should be included in the feasibility study. We anticipate that we will randomize approximately 100 leaders in the full-scale trial. Thus, we will include 10 patients in the feasibility trial.

Data Analysis and Storage: A description of feasibility outcomes will be presented, including leader eligibility and recruitment, leader enrolment and randomization, technological performance of the videoconferencing system, and treatment fidelity. Qualitative information will inform any necessary changes to the program or trial methods before conducting a full-scale trial. Descriptive statistics will be used to provide means and standard deviations for SPIN-SSLED Program outcome measures.

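### Attendance, withdrawal with reasons and 3-month completion are not planned for reporting, and leaders who complete no module are not invited to interview

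*Combined protocol and SAP*

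**What the plan says.** In Section 6, SPIN-SSLED Feasibility Measures, the words "The collected measures of feasibility include" introduce five items: how enrolment and randomisation work, consent ("The percentage of eligible group leaders who consent to participation"), staff effort to help leaders online, difficulties met by staff, and performance of the video platform. Delivery fidelity is added: "Raters will evaluate adherence to each session's goals and content". Interviews after the last module cover accessibility, obstacles to taking part and feedback, under this entry rule: "Participants who have completed any of the 13 modules will be asked to participate in the interviews".

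Under SPIN-SSLED Program Outcome Measures, questionnaires fall due at allocation and "after completion of the Program (3 months post".

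The Data Analysis and Storage paragraph promises a description of "leader eligibility and recruitment, leader enrolment and randomization, technological performance of the videoconferencing system, and treatment fidelity". For the questionnaires it says "Descriptive statistics will be used to provide means and standard deviations for SPIN-SSLED Program outcome measures".

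The examples of scientific aspects in Sections 1 and 3 are recruitment, fidelity, acceptability and how the outcome measures perform. No section names attendance, withdrawal or questionnaire completion as something to be reported.

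**The concern.** The first research question in Section 1 is whether the full-scale randomised trial can be done. That trial needs leaders to follow 13 live modules of 60 to 90 minutes over 3 months and then fill in the self-efficacy scale, its primary outcome. Consent shows who starts, and fidelity shows what was delivered. A session can score well on fidelity with few leaders present. Nothing in the reporting plan shows who stayed, who answered at 3 months, or why anyone left. Training groups have only 5 leaders and rely on guided discussion, so an absence also affects those who attend.

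The interview rule adds to the gap. Obstacles to taking part are an interview topic, yet the leaders likely to know most about them, those who completed no module, are not invited.

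**Working it through.** **Step 1. The plan's own figure.** The sample size paragraph takes about 10% of a full-scale trial of about 100: 0.10 × 100 = 10. This reproduces. No drop-out rate or allowance accompanies the 100.

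**Step 2. Lists side by side.**

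| Item | In the Section 6 measures | In the analysis paragraph | Recoverable afterwards |
|---|---|---|---|
| Consent percentage | yes | yes, within recruitment | not needed |
| Delivery fidelity | yes | yes | not needed |
| Modules attended per leader | no | no | largely, from recordings |
| Questionnaire completion, baseline and 3 months | no | no | yes, from the survey database |
| Withdrawal: reason | no | no | no |
| Views of leaders with no module completed | excluded by the interview rule | no | no |

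The volume is small: 2 groups × 13 modules = 26 sessions, and 10 leaders × 13 modules = 130 leader-sessions.

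**Step 3. Chance that a loss is seen at all.** If each leader independently has probability p of being lost, the chance of at least one loss among 10 is 1 − (1 − p)^10. The documents give no p, so these values are assumptions:

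- p = 5%: 1 − 0.95^10 = 40%
- p = 10%: 1 − 0.90^10 = 65%
- p = 20%: 1 − 0.80^10 = 89%

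The same formula applies to the chance that at least one leader completes no module, with p as the probability of that event.

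**Step 4. Precision of a completion rate from 10 leaders.** For x of n, the exact (Clopper-Pearson) 95% limits are the 2.5% quantile of Beta(x, n − x + 1) and the 97.5% quantile of Beta(x + 1, n − x). For 10 of 10 the upper limit is 100%.

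| Completed | Rate | Exact 95% interval |
|---|---|---|
| 10/10 | 100% | 69% to 100% |
| 9/10 | 90% | 55% to 99.7% |
| 8/10 | 80% | 44% to 97% |
| 7/10 | 70% | 35% to 93% |

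**Step 5. What this can and cannot tell the full-scale trial.** At assumed losses of 10%, 20% and 30%, 100 randomised leaders leave 90, 80 and 70 with the primary outcome. Keeping 100 with data would need 100/(1 − loss), rounded up: 112, 125 and 143. The intervals in Step 4 are too wide to choose between these: 9/10 is compatible with 70% completion and 7/10 with 90%. The counts are therefore descriptive and do not give a planning rate for drop-out. Section 4 puts all 10 leaders into training, so they also carry no information on the wait-list arm.

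**The case against.** The case on the other side is substantial. Both lists are worded as non-exhaustive, and the stated aims of acceptability and outcome performance could take in attendance and completion. Questionnaires are scheduled at both time points and go into a database meant to hold all responses. Sessions are video-recorded, and the interview rule cannot be applied without knowing who completed what. Eligibility requires availability at the session times. A leader who leaves after one module is still invited to interview. Section 2 also speaks of interviewing the 10 leaders who took part in the training, which suggests that near-complete coverage was intended.

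Most of this stands, and it rules out several stronger readings that a reader might infer:

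- That retention goes unmeasured. The raw data for attendance and completion would largely exist; what is missing is a planned report with a definition and a denominator.
- That the trial could be declared feasible with half the leaders absent. With 10 people and recorded sessions, such a loss would be hard to miss.
- That the 3-month questionnaire goes only to completers. Section 4 sends the survey link to every participant, and the Section 6 wording reads as a time point.
- That completion is a main driver of the full-scale trial's power. Under 50:50 allocation, two-sided 5%, 80% power and no clustering, the detectable difference moves only from 0.57 SD with 100 completers to 0.60 SD with 90. The documents state none of those power, significance or allocation figures, and Section 4 says clustering must be allowed for.
- That burden on leaders is given as the sole cause of group failure. Section 1 names it as one factor among others, and it concerns running a support group, not attending training.

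The objection does not reach two items. Recordings and survey exports do not show why someone withdrew, and the interview rule as written leaves out anyone with no module completed. Section 2 does not settle this, since it too refers to those who took part.

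**Conclusion.** The point holds as a gap in planned reporting and in interview coverage. Two kinds of information would be lost under the plan as written: reasons for withdrawal and the views of leaders who complete no module. Two others, attendance and questionnaire completion, are recoverable but not promised. How much is lost depends on how many leaders withdraw or never start, which the documents do not indicate; it could be none. This is a low-cost improvement that bears directly on the trial's first question, and it does not undermine the design. The probabilities in Step 3 rest on assumed rates and independence between leaders; the reading of the two lists does not.

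**What to change.** 1. Change the interview rule in Section 6 so that all 10 allocated leaders are invited, whatever number of modules they completed, and bring the interview sentence in Section 2 into line.
2. Add a withdrawal record to the feasibility measures: when each leader left and, where the leader is willing to say, why.
3. Add to both the measures list and the Data Analysis and Storage paragraph a descriptive report, with all 10 as denominator, of modules attended out of 13 per leader and of the number completing each outcome measure at baseline and at 3 months.
4. State the limits beside the results: rates from 10 leaders are imprecise and should be shown with exact intervals, and they describe trained leaders only.

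The cost is an attendance log for 26 sessions, a short withdrawal form, a few lines of text and up to a few extra interview invitations. Design, sample size and program are unchanged.

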PROTOCOL TITLE:

**The Scleroderma Patient-centered Intervention Network (SPIN) - Scleroderma Support group
Leader Education (SSLED) Program Feasibility Trial**

NCT03508661

February 1, 2018

PROTOCOL TITLE:

The Scleroderma Patient-centered Intervention Network (SPIN) - Scleroderma Support group Leader EDucation (SSLED) Program Feasibility Trial

1. Overview

Many people living with a rare disease turn to peer-led support groups to cope with their condition and access educational resources.¹⁻³ Systemic sclerosis (SSc), or scleroderma, is a rare autoimmune connective tissue disease where peer-led support groups play an important role.^{2,4,6,7} There are currently approximately 200 SSc support groups in Canada and the US, most of which are led by people with SSc.^{8,9} Many SSc patients, however, cannot access support groups. In other cases, support groups are not sustained due to factors that include the burden on group leaders living with a serious, unpredictable disease and limited group leadership skills of some untrained leaders.^{3,4,10} Our partners from Scleroderma Canada and the Scleroderma Foundation in the US are committed to improving support group accessibility and effectiveness. These organizations maintain a list of active support groups, but currently do not provide training or other resources to groups or their leaders. To address this gap, our team, including investigators and patients from the Scleroderma Patient-centered Intervention Network (SPIN), developed the Scleroderma Support group Leader EDucation (SPIN-SSLED) Program, which is designed to improve support group leader confidence and self-efficacy, reduce burnout, improve emotional well-being, and improve health-related quality of life.

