Scleroderma Canada and the Scleroderma Foundation are committed to developing a shared infrastructure to improve support groups effectiveness and accessibility, including the quality of existing support groups and increasing the availability of support group services by training new leaders to initiate support groups in underserved areas and via the internet. These organizations have partnered with our team to develop and test the SPIN-SSLED Program, a 3-month-long group training program designed to be delivered via videoconferencing to provide information and skills to improve leader support group leaders' confidence and self-efficacy to carry out their leadership roles and reduce the burden on them of leading a support group. If effective, the organizations will adopt the SPIN-SSLED Program to provide ongoing training for support group leaders.

To better understand reasons for attending and not attending support groups and support group leader training needs, we conducted one-on-one interviews with 30 support group members, non-attenders, and leaders. We then developed a survey, which was completed by 600 North American and 700 European and Australian SSc patients (approximately 45% non-attenders, 40% group members, and 15% leaders; manuscripts in press⁴, submitted for review, or in preparation). The proposed SPIN-SSLED Program Feasibility Trial builds on this background research and will evaluate the feasibility of delivering the SPIN-SSLED Program and of our planned full-scale trial design. We will enroll 10 SSc support group leaders and randomly allocate 10 into 2 SPIN-SSLED Program training groups (5 leaders per group). At

the end of the feasibility trial intervention, we will interview the 10 group leaders who took part in the training in order to identify aspects of the program that might be improved. We will use this information to make any necessary revisions to the program or our trial methods before conducting a full-scale trial.

3. Objectives

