Participants: To be eligible for the SPIN-SSLED Feasibility Trial leaders must be a current SSc support group leader or have been identified by Scleroderma Canada or the Scleroderma Foundation as a new leader who will initiate a new support group, must be able to use the internet to access and participate in training sessions and to complete study questionnaires online, must be available to participate at times when sessions are scheduled and be English-speaking. Individuals who are offered participation in the feasibility study will be excluded from the subsequent full-scale RCT. As the majority of leaders who are members of the organizations from which we are recruiting are English-speaking, in order to ensure that there will be an adequate number of French-speaking participants in the RCT, only English-speaking leaders will be included in the feasibility study. Therefore, for the proposed feasibility study, only English-speaking leaders will be recruited, and the resulting program will be subsequently translated into French. The full-scale trial will be conducted in English and French.

Recruitment, Consent and Randomization: Our partners from the Scleroderma Canada and the Scleroderma Foundation will contact group leaders to describe the SPIN-SSLED Feasibility Trial and ascertain interest in participating. SPIN-SSLED personnel will send email invitations with the consent form to interested support group leaders. Following this, support group leaders will be contacted by phone within 48 hours to describe the study, review the consent form, and answer questions assessing

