eligibility. Eligible patients who verbally accept the offer to enrol in the study will receive an email with the consent form for the study, which they can sign by replying, “**I have read the consent form and understand the terms of the feasibility study. I agree to participate in the study testing the feasibility of the SPIN-SSLED Program.**” We will enrol 10 English-speaking SSc support group leaders who we will randomly assign to 2 SPIN-SSLED Program training groups (5 leaders per group). All participants will receive an email invitation including a clickable link to the online survey platform Qualtrics where they will be asked to complete study measures. The email will also include the date of leaders’ first training session, the topic of the first session and information on how to login to the videoconferencing system. Email and phone technical support will be available to help leaders with the consent process, when they access Qualtrics to complete study measures, and for training sessions.

5. Intervention

The SPIN-SSLED Program was developed by a team of researchers with expertise in SSc, patient organization representatives, and a Patient Advisory Board comprised of current SSc support group leaders. The program content and design is based on results of our preliminary research on support groups in SSc and informed by instructional material for support group leaders we identified via the internet and by consultations with support group leaders. The program uses a problem-based learning approach. Problem-based learning is a learner-centered approach that integrates theory and practice by providing the necessary knowledge and skills, presenting a complex, real-world problem, then working to identify an approach to solving the problem.^{29,30} To implement this, each module, or learning session, will introduce a topic and provide an overview of key information. Then, there will be a guided discussion among training group participants about possible approaches and solutions.

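### The interviews are meant to assess barriers to participating, but the only invitation rule requires at least one completed module, so an allocated leader who completes none is not among those to be asked

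*Combined protocol and SAP*

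**What the plan says.** Section 6 (Measures), under SPIN-SSLED Feasibility Measures, says individual interviews will be held once the 13 modules are finished. They are "to assess the accessibility of the intervention, barriers to participating, and user feedback", and they also explore how leaders experienced the program. The next sentence says who is invited: "Participants who have completed any of the 13 modules will be asked to participate in the interviews".

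Two other places mention the interviews. The end of Section 2 (Background and Rationale) says "we will interview the 10 group leaders who took part in the training". Section 9 (Risks and Potential Benefits) names a post-program interview as one part of taking part in the trial and sets no condition on who is asked.

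On allocation, Section 4 says "We will enrol 10 English-speaking SSc support group leaders who we will randomly assign to 2 SPIN-SSLED Program training groups (5 leaders per group)". Participants are told the date of their first session by email as part of the enrolment steps.

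On use of the results, Section 6 under Data Analysis and Storage says "Qualitative information will inform any necessary changes to the program or trial methods before conducting a full-scale trial".

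**The concern.** One aim of the interviews is to learn what keeps leaders from participating, but the invitation depends on having participated. Leaders who met the strongest barrier, one that kept them from completing even a single module, are the ones the rule does not reach. They cannot comment on program content, but they have first-hand knowledge of what kept them out.

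At stake is part of the evidence for the trial's own question, namely whether the program or the trial methods need changing before about 100 leaders are randomized. A barrier to starting bears on recruitment, scheduling and access, all of which the full-scale trial will face again. Section 4 excludes anyone offered the feasibility study from the later trial, so a non-starter missed here will not be heard there as a participant. No estimate, sample size or other numerical result depends on the rule.

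**Working it through.** **Step 1: the plan's own figure.** Section 6 (Sample size) takes about 10% of an anticipated 100 leaders: 0.10 × 100 = 10. Section 4 has 2 groups of 5: 2 × 5 = 10. The two agree, and this point does not dispute the figure.

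**Step 2: who the wording covers.**

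| Leader's status | Invited under the Section 6 rule? |
|---|---|
| Completed all 13 modules | Yes |
| Stopped after 1 to 12 modules | Yes, one module is enough |
| Allocated, completed no module | Not among those to be asked |

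The last row can occur because enrolment and allocation come before the first session. The documents do not define completing a module, so on a literal reading the row also holds a leader who joins one session but does not finish it.

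**Step 3: whether another section gives such a leader a route.**

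- Section 2 speaks of the 10 leaders who took part in the training. It assumes all 10 do so and is itself tied to participation.
- Section 9 mentions the interview but sets no invitation rule.
- The feasibility list in Section 6 counts the percentage of eligible leaders who consent. It has no item for starting, attendance or reasons for not starting.

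No route is stated.

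**Step 4: how often it could matter.** The documents give no non-start rate. Let p be the assumed chance that an allocated leader completes no module, with n = 10 and leaders treated as independent.

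- Expected number outside the rule = 10p
- P(at least one) = 1 − (1 − p)^10
- P(none or one) = (1 − p)^10 + 10p(1 − p)^9

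| Assumed p | Expected of 10 | P(at least one) | P(none or one) |
|---|---|---|---|
| 0% | 0 | 0 | 1 |
| 5% | 0.5 | 1 − 0.95^10 = 0.40 | 0.91 |
| 10% | 1 | 1 − 0.90^10 = 0.65 | 0.74 |
| 20% | 2 | 1 − 0.80^10 = 0.89 | 0.38 |

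**Step 5: coverage if there is one non-starter.** The current rule covers 9 of 10 allocated leaders (90%) and 0 of 1 non-starters. Inviting all allocated leaders covers 10 of 10 and 1 of 1. One leader is 1/5 = 20% of a training group.

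**The case against.** The strongest case on the other side is that this is an unaddressed edge case in a generous rule. The sentence does not say that only these leaders will be interviewed, and one completed module is enough. Sections 2 and 9 suggest an intention to interview all 10. This stands as a limit. A reader might infer that the plan deliberately shuts non-starters out, and the documents do not support that. The Section 6 sentence is still the only invitation rule, and staff who follow it would have no instruction to approach a non-starter.

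A second argument is that some exposure is needed to give feedback or describe the experience of the program. That is right for those two aims. It does not hold for accessibility and barriers, which a non-starter can speak to.

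A third argument is that reasons for not starting may surface elsewhere. Section 6 assesses process throughout the trial, including how enrolment and randomization work, challenges for personnel and the performance of the videoconferencing system. Section 4 offers technical support, and an absence from a group of 5 would be noticed. This also stands in part. A reader might infer that barriers to starting would be lost altogether, and that goes too far. What is lacking is systematic collection of the leader's own account.

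Finally, non-start may be rare. Eligibility requires that leaders "must be available to participate at times when sessions are scheduled". A reader might set against this the wording in Section 1 about "the burden on group leaders living with a serious, unpredictable disease". That wording explains why support groups are not sustained and is no evidence about failing to start this training. The documents settle the rate in neither direction.

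**Conclusion.** The point holds as a minor mismatch between a stated aim and a stated rule. An allocated leader with no completed module is not among those to be asked, and no other section supplies a route. This rests on the wording alone and is firm.

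The size is not firm. It depends on a non-start rate the documents do not give and on leaders acting independently. Across assumed rates of 0% to 20%, the expected number outside the rule runs from 0 to 2 of 10. A reader might infer that at most one leader is likely to be affected. That follows only if the rate is taken to be low: the chance of none or one is 0.91 at 5% but 0.38 at 20%. If every leader completes at least one module, the rule makes no difference. The change is worth considering because it is cheap and serves the trial's own feasibility question.

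**What to change.** In Section 6, under SPIN-SSLED Feasibility Measures, replace the invitation sentence with one that invites every allocated leader who has not withdrawn consent to contact, regardless of modules completed. Limit the interview of a leader with no completed module to accessibility and barriers. Record the reason for not starting when it becomes known, since waiting until the 13 modules are over could put the question about three months after the event. Align the Section 2 sentence on who is interviewed with the new rule.

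The cost is one revised sentence with a matching edit in Section 2, a short alternative interview guide and one data field. Some non-starters may decline, so the change makes it possible to collect their account but does not guarantee it. The total stays within the 10 interviews already planned.
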